1 PROTOCOL SUMMARY

1.1 SYNOPSIS

Title: A multi-center, randomized, double blind, parallel-arm, placebo controlled trial of mepolizumab for treatment of adults and adolescents with active eosinophilic esophagitis and dysphagia-predominant symptoms

Study Description: This multi-center, randomized, double blind, parallel-arm, placebo controlled trial will determine whether mepolizumab is more effective than placebo for improving symptoms of dysphagia and decreasing esophageal eosinophil counts in adults and adolescents with active eosinophilic esophagitis after an initial 3-month treatment course and will also assess the impact of an additional 3-months of treatment.

Objectives: Primary Objectives:

1. To determine whether mepolizumab is more effective than placebo for improving symptoms of dysphagia as measured by the validated Eosinophilic Esophagitis Symptom Activity Index (EEsAI) in adults and adolescents with active eosinophilic esophagitis after a 3-month treatment course.
2. To determine whether mepolizumab is more effective than placebo for decreasing esophageal eosinophil counts in adults and adolescents with active eosinophilic esophagitis after a 3-month treatment course.

Secondary Objectives:

1. To determine predictors of symptomatic and histologic response to mepolizumab treatment, including potential biomarkers.
2. To assess durability of symptomatic and histologic response to mepolizumab after 6 months of treatment in patients initially randomized to the active medication (this includes a 3-month blinded second phase of treatment).
3. To assess histologic response to a lower dose of mepolizumab treatment in patients initially randomized to the placebo arm (this will be in a 3-month blinded second phase); symptom response will also be assessed in this phase.
4. To assess safety of mepolizumab over 3 and 6 months of treatment (this includes both 3-month study phases).

Outcomes:

Primary Outcome:

1. Mean change in dysphagia as measured by the EEsAI score (7-day recall) from baseline to 3-months post-treatment.

Secondary Outcomes:

1. Proportion of patients who have clinical remission as defined by an EEsAI score of ≤ 20 .
2. Proportion of patients who have a clinical response, as defined by an EEsAI score decrease of ≥ 20 points.
3. Absolute peak eosinophil count (measured in eos/hpf) after 3-months of treatment.
4. Levels of histologic response after 3-months of treatment including < 15 , ≤ 6 , and ≤ 1 eos/hpf.

[figure not shown]

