5. Mean change in severity of endoscopic findings as measured by the EoE Endoscopic Reference Score (EREFS) from baseline to 3-months post-treatment.
6. Mean change in the Straumann Dysphagia Instrument (SDI) from baseline to 3-months post-treatment.

Prespecified Exploratory Outcomes

1. Mean change in peripheral blood eosinophil levels from baseline to 3-months post treatment.
2. For patients initially randomized to active medication, the same set of outcomes (as listed above) will be assessed after 6 months of treatment.
3. For patients initially randomized to placebo, a paired analysis will be conducted to compare month 6 to month 3 outcomes.
4. For the same set of outcomes (as listed above), 3-month data for patients initially randomized to active medication (300mg monthly) will be compared to 6 month data for patients initially randomized to placebo and who have completed 3-months of 100mg monthly. This will provide a comparison of the 300mg to the 100mg dose.
5. Adverse events and safety during all time points in the study.

Study Population:	72 adult and adolescent patients with active EoE as measured by both symptomatic and histologic severity.
Phase:	2
Description of Sites/Facilities Enrolling Participants:	4 United States sites. Competitive enrollment.
Description of Study Intervention:	Arm 1: Mepolizumab 300 mg SQ monthly for 6 months. Arm 2: Placebo SQ monthly for 3-months followed by mepolizumab 100mg SQ monthly for 3 months. (Note that both arms are blinded for the entire 6 months)
Study Duration:	3 years
Participant Duration:	10 months

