4 STUDY DESIGN

4.1 OVERALL DESIGN

This is a multi-center, randomized, double blind, parallel-arm, placebo controlled trial of mepolizumab. After the first 3-month blinded phase, there will be a second 3-month blinded phase where all patients receive active medication, but the dose will be lower in the subjects initially randomized to the placebo arm.

In the first arm, subjects will receive mepolizumab 300 mg SQ monthly for 3 months. In the second arm, subjects will receive a placebo SQ injection monthly for 3 months. Both groups will have the injection administered under direct observation in a clinical setting to ensure proper administration and compliance. Each visit will also provide an opportunity for symptom questionnaires to be completed and for blood samples to be drawn. After 3-months (the time point where the primary outcome is assessed), all subjects initially randomized to active treatment will continue with mepolizumab dosing 300 mg SQ monthly and will remain blinded. All subjects initially randomized to placebo will receive mepolizumab 100mg SQ monthly and will remain blinded.

Of note, no dietary changes, dilations, changes in baseline PPI medication dose, changes in inhaled or intranasal steroid doses, or administration or oral, topical/swallowed, or systemic steroids will be allowed during the study period (from consent through the end of treatment period). Subjects will undergo endoscopy after the first blinded phase (at 3 months) and after the second blinded phase (after 6 months).

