9.3 POPULATIONS FOR ANALYSES

The analysis dataset will be modified intention to treat (ITT), which will include all participants who received study drug and who have 3-month outcome data for EEsAI and endoscopy. We will have a secondary analysis dataset for a sensitivity analysis where the last available EEsAI value will be carried forward for any participants who terminate the study or are lost to follow-up.

The safety analysis dataset will be all participants who received study drug, regardless of follow-up time or other outcomes.

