9.4.4 SAFETY ANALYSES

All treatment emergent adverse events will be tabulated and summarized between the study groups and presented in a series of tables using standard Medical Dictionary for Regulatory Activities (MedDRA) terminology.

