9.4.9 EXPLORATORY ANALYSES

Prespecified exploratory outcomes are as follows:

- Mean change in peripheral blood eosinophil levels from baseline to 3-months post-treatment. This will be compared between the groups using analysis of covariance.
- For patients initially randomized to active medication, the same set of outcomes (as listed above) will be assessed after 6 months of treatment. This will be compared between the groups using analysis of covariance.
- For patients initially randomized to placebo, a paired analysis will be conducted to compare month 3 to month 6 outcomes. This will use paired t-tests for continuous variables and McNemar's test for categorical variables.
- For the same set of outcomes (as listed above), 3-month data for patients initially randomized to active medication (300mg monthly) will be compared to 6 month data for patients initially randomized to placebo and who have completed 3-months of 100mg monthly. This will provide a comparison of the 300mg to the 100mg dose.
- Adverse events and safety during all time points in the study. This will be compared between groups by chi-square.

Additional Exploratory outcomes are as follows:

- Change in weekly SDI score over the course of the study, and correlation of SDI with the EEsAI score. We will also explore the minimal clinically important differences (MCIDs) of these measures.
- Biomarkers, including serum and tissue levels of cytokines and related factors (IL-5, IL-13, and eotaxin-3 [CCL26]), and eosinophil granule levels (i.e. eosinophil peroxidase or major basic protein) in blood and tissue.
- Antibodies to mepolizumab as a measure of immunogenicity. The study sponsor will assist with these measurements.
- Additional histologic findings, including eosinophil degranulation, microabscesses, basal layer hyperplasia, spongiosis, and lamina propria fibrosis (in samples with adequate subepithelial tissue present).

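### The planned whole-study comparison of adverse events by randomised group does not estimate mepolizumab versus placebo, because the placebo arm takes mepolizumab 100 mg from month 3

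*Combined protocol and SAP*

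**What the plan says.** The only between-group safety test in the plan is the last prespecified exploratory outcome in section 9.4.9: "Adverse events and safety during all time points in the study. This will be compared between groups by chi-square". Section 9.4.4 gives the main tabulation: "All treatment emergent adverse events will be tabulated and summarized between the study groups". Section 9.3 defines who is counted: "The safety analysis dataset will be all participants who received study drug, regardless of follow-up time or other outcomes". None of the three sets a cut at month 3, attributes an event to the treatment in use at onset, or adjusts for time on treatment.

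The synopsis describes the arms as "Arm 1: Mepolizumab 300 mg SQ monthly for 6 months" and "Arm 2: Placebo SQ monthly for 3-months followed by mepolizumab 100mg SQ monthly for 3 months". Section 4.1 confirms that "there will be a second 3-month blinded phase where all patients receive active medication", and section 6.1.2 places the switch at the 3-month visit. Secondary objective 4 concerns the safety of mepolizumab over 3 and 6 months, but no analysis rule carries those two horizons into the adverse-event comparison.

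**The concern.** Months 0-3 are the only period in which mepolizumab is compared with placebo under randomisation, and the plan never isolates them for adverse events. A comparison over the whole study by randomised group mixes that period with one in which both arms take active drug, and then with follow-up in which neither arm does. An event that begins on 100 mg in month 4 is counted in the originally-placebo group.

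At stake is the interpretation of the safety result. A ratio near 1 from this table could be reported as no excess over placebo, when the comparison group spent half its treatment time on the drug. Other bullets in section 9.4.9 do name the month and the dose (month 3 against month 6 in the placebo arm; 300 mg at 3 months against 100 mg at 6 months). They apply to the outcomes listed before the adverse-event bullet, so they do not supply the missing rule.

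**Working it through.** **The plan's own figures.** The plan gives no expected rate or power for the safety comparison, so there is no stated safety figure to reproduce. Its one sizing result (30 per group for a 17-point EEsAI difference, SD 20, power 0.9) does reproduce, with power 0.909, but has no bearing here.

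**Inputs, all from section 2.2.1.**
- Injection-site reactions: 8% on 100 mg v 3% on placebo. At 300 mg, 7% v 4% in the HES trials and 15% v 13% in the EGPA trials.
- Systemic reactions: 3% on 100 mg v 5% on placebo. At 300 mg, 6% v 1% in EGPA.
- The list of common adverse reactions gives the same 8% (3%) for the first 24 weeks of two asthma trials.

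**Assumptions.** Each rate is the risk of at least one event per 3-month phase (except row B), and phases are independent. The 100 mg risk is set equal to the 300 mg risk, except in rows E and F.

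**Formulas.** Let p0, p300 and p100 be the per-phase risks.
- Months 0-3: p300 v p0.
- Months 0-6 by arm: 1-(1-p300)² v 1-(1-p0)(1-p100).
- Row A: 1-0.92² = 0.1536 and 1-0.97×0.92 = 0.1076. The ratio is 1.43 and the difference 4.6 points.
- Row B reads 8% v 3% as risks over the whole six months (24 weeks is slightly less). Per phase this gives 1-√0.92 = 4.1% and 1-√0.97 = 1.5%.

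| Row | p0 / p300 / p100 | Months 0-3: ratio (difference) | Months 0-6 by arm | Ratio (difference) |
|---|---|---|---|---|
| A. Injection site, 100 mg rates | 3 / 8 / 8% | 2.67 (5.0 points) | 15.36% v 10.76% | 1.43 (4.6) |
| B. As A, read as 24-week risks | 1.5 / 4.1 / 4.1% | 2.70 (2.6) | 8.00% v 5.53% | 1.45 (2.5) |
| C. Injection site, HES | 4 / 7 / 7% | 1.75 (3.0) | 13.51% v 10.72% | 1.26 (2.8) |
| D. Injection site, EGPA | 13 / 15 / 15% | 1.15 (2.0) | 27.75% v 26.05% | 1.07 (1.7) |
| E. Systemic, intermediate 100 mg risk | 1 / 6 / 3% | 6.00 (5.0) | 11.64% v 3.97% | 2.93 (7.7) |
| F. Systemic, 100 mg as placebo | 1 / 6 / 1% | 6.00 (5.0) | 11.64% v 1.99% | 5.85 (9.7) |

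Row E takes its 300 mg and placebo rates from one set of trials and its 100 mg rate from another, so it shows only what an intermediate risk would do.

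**Reading the table.** With equal risk p at both doses, the six-month difference is (1-p)(p-p0), that is, (1-p) times the 3-month difference. In row A this is 0.92×5.0 = 4.6 points. For rare events the absolute difference therefore hardly changes, while the ratio falls markedly. With an intermediate 100 mg risk (row E) the ratio still falls but the difference grows. With placebo-level risk on 100 mg (row F) the result is the same as if placebo had continued.

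**Power.** For the exact uncorrected chi-square test with 36 per arm, power in months 0-3 is 0.135 (row A), 0.035 (row B), 0.074 (row C) and 0.061 (row D). By arm over six months it is 0.094, 0.070, 0.072 and 0.053.

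**The case against.** The strongest objection concerns direction. Dilution needs 100 mg to raise risk above placebo. The injection-site rates point that way, but section 2.2.1 reports systemic reactions less often on 100 mg (3%) than on placebo (5%). For such events the switch does not dilute the contrast and could widen it. A reader might infer that the comparison is always biased towards no difference; the documents do not support that.

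A reader might also infer that about half of the risk difference is lost. That is true only against placebo continued to six months (row A: 9.45 points against 4.6), which neither this trial nor any reanalysis of it can supply. Against months 0-3, the window that can be used, the change is from 5.0 to 4.6 points.

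The size also depends on which rates are chosen. The 8% v 3% contrast belongs to 100 mg and appears elsewhere as a 24-week figure. The 300 mg rates give smaller ratios in both windows (rows C and D).

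The wording leaves some room too: the phrase about all time points could mean at each time point, and objective 4 names both horizons. But the text does not fix that reading, and it would still need a rule for the period after month 3.

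Finally, the test is exploratory and has low power in either window. Participant protection does not rest on it, since the DSMB reviews serious events as reported and all adverse events at set meetings (section 9.4.6). These points limit the consequence. None of them makes the whole-study contrast an estimate of drug versus placebo.

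**Conclusion.** The point holds in a limited form and should be corrected. As written, the adverse-event comparison contrasts six months of 300 mg with a placebo-then-100 mg sequence, and the one placebo-controlled window is not separated. That follows from the text and the design and needs no assumption about rates.

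The numerical effect is conditional. If both doses carry equal risk, the injection-site ratio falls from 2.7 to about 1.4 on the 100 mg rates, whether these are read as 3-month or 24-week risks, and from 1.75 to 1.26 on the HES rates. The absolute difference for rare events changes little. If 100 mg carries no excess risk, there is no dilution. The practical harm is a misleading estimate and label more than lost power.

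**What to change.** State in sections 9.4.4 and 9.4.9 that:

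1. The drug-placebo safety comparison uses events with onset from first dose until before the month-3 dose, 300 mg against placebo.
2. Later events during dosing are tabulated by treatment received at onset (300 mg or 100 mg), with incidence per patient-month.
3. Events in off-drug follow-up, after a participant's last dosing period, are shown separately by last treatment received. This is needed because the month 8 visit falls three months after the last dose (section 8.7).
4. Any whole-study comparison is descriptive, labelled by treatment sequence, and not described as mepolizumab versus placebo. A comparison of sequences is legitimate when it is named as one.

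No new data are required: section 8.8.5 already records time of onset, and the month-3 dose is a clear cut-point. The cost is SAP wording and a few more table columns. The analysis remains exploratory with low power, and the shorter window will contain fewer events.

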10 SUPPORTING DOCUMENTATION AND OPERATIONAL CONSIDERATIONS

10.1 REGULATORY, ETHICAL, AND STUDY OVERSIGHT CONSIDERATIONS

10.1.1 INFORMED CONSENT PROCESS

10.1.1.1 CONSENT/ASSENT AND OTHER INFORMATIONAL DOCUMENTS PROVIDED TO PARTICIPANTS

Consent forms describing in detail the study intervention, study procedures, and risks are given to the participant and written documentation of informed consent is required prior to starting intervention/administering study intervention.

10.1.1.2 CONSENT PROCEDURES AND DOCUMENTATION

Informed consent is a process that is initiated prior to the individual's agreeing to participate in the study and continues throughout the participant's study participation. Consent forms will be IRB - approved and the participant will be asked to read and review the document(s). The investigator or approved study staff will explain the research study to the participant and answer any questions that may arise. A verbal explanation will be provided in terms suited to the participant's comprehension of the purposes, procedures, and potential risks of the study and of their rights as research participants. Participants will have the opportunity to carefully review the written consent form(s) and ask questions prior to signing. The participants should have the opportunity to discuss the study with their family or surrogates or think about it prior to agreeing to participate. The participant will sign the informed consent document(s) prior to any procedures being done specifically for the study. Participants must be informed that participation is voluntary and that they may withdraw from the study at any time, without prejudice. A copy of the informed consent document(s) will be given to the participants for their records. The informed consent process will be conducted and documented in the source document (including the date), and the form signed, before the participant undergoes any study-specific procedures. The rights and welfare of the participants will be protected by emphasizing to them that the quality of their medical care will not be adversely affected if they decline to participate in this study.

10.1.2 STUDY DISCONTINUATION AND CLOSURE

This trial must suspend screening and enrollment and confer immediately with the DSMB in the event of any of the following:

- A grade 4 (life-threatening consequences; urgent intervention indicated) AE that is related or possibly related to treatment as determined by the sponsor-investigator
- A grade 5 (Death related to AE) AE that is related or possibly related to treatment as determined by the sponsor-investigator
- New information leading to unfavorable risk-benefit judgment of the study drug, e.g., significant previously unknown adverse reactions or unexpectedly high intensity or incidence of known adverse reactions, or other unfavorable safety findings
- A decision that continuation of the trial is unjustifiable for medical or ethical reasons

A grade 3 (severe or medically significant but not immediately life-threatening; hospitalization or prolongation of hospitalization) AE that is related or possibly related (per the UNC IRB definition of

relatedness) to the study intervention will be immediately reported to the DSMB for review and screening and enrollment will continue unless the DSMB rules otherwise upon their review of the event. If two grade 3 related or possibly related events occur, screening and enrollment will be suspended at the time of the event and the DSMB will review all AE data at that time. Screening and enrolment may resume pending DSMB determination that it is appropriate to continue.

Upon a determination that continuation of the trial is unjustifiable for medical or ethical reasons, all study activities may be suspended. Written notification, documenting the reason for study suspension or termination, will be provided by the suspending or terminating party to study participants, investigator(s), funding agency, the IND sponsor, and regulatory authorities; as applicable. If the study is prematurely terminated or suspended, the investigator will promptly inform study participants, the IRB, and sponsor and will provide the reason(s) for the termination or suspension. Study participants will be contacted, as applicable, and be informed of changes to study visit schedule.

Study may resume once concerns about safety, protocol compliance, and data quality are addressed, and satisfy the sponsor, IRB and/or FDA.

10.1.3 CONFIDENTIALITY AND PRIVACY

Participant confidentiality and privacy is strictly held in trust by the participating investigators, their staff, the sponsor(s), and their institutions. This confidentiality is extended to cover testing of biological samples and genetic tests in addition to the clinical information relating to participants. Therefore, the study protocol, documentation, data, and all other information generated will be held in strict confidence. No information concerning the study or the data will be released to any unauthorized third party without prior written approval of the sponsor and documented written consent from participants.

All research activities will be conducted in as private a setting as possible.

The study monitor, other authorized representatives of the sponsor, representatives of the IRB, regulatory agencies or pharmaceutical company supplying study product may inspect all documents and records required to be maintained by the investigator, including but not limited to, medical records (office, clinic, or hospital) and pharmacy records for the participants in this study. The clinical study site will permit access to such records.

The study participant's contact information will be securely stored at each clinical site for internal use during the study. At the end of the study, all records will continue to be kept in a secure location for as long a period as dictated by the reviewing IRB, Institutional policies, and sponsor requirements.

Study participant research data, which is for purposes of statistical analysis and scientific reporting, will be transmitted to and stored at the University of North Carolina at Chapel Hill. This will not include the participant's contact or identifying information. Rather, individual participants and their research data will be identified by a unique study identification number. The study data entry and study management systems used by clinical sites and by the University of North Carolina at Chapel Hill research staff will be secured and password protected. At the end of the study, all study databases will be coded and archived at the University of North Carolina at Chapel Hill.

10.1.4 FUTURE USE OF STORED SPECIMENS AND DATA

Data collected for this study will be analyzed and stored at the University of North Carolina at Chapel Hill. After the study is completed, the coded, archived data will continue to be stored at the University of North Carolina at Chapel Hill for use by other researchers including those outside of the study. Permission to store and transmit data and specimens will be included in the informed consent.

With the participant's approval and as approved by local IRBs, coded biological samples will be stored at the University of North Carolina at Chapel Hill. These samples could be used to research the causes of EoE, its complications and other conditions for which individuals with EoE are at increased risk, and to improve treatment. Other researchers will also be provided with a code-link that will allow linking the biological specimens with the phenotypic data from each participant, maintaining the blinding of the identity of the participant.

During the conduct of the study, an individual participant can choose to withdraw consent to have biological specimens stored for future research. However, withdrawal of consent with regard to biosample storage may not be possible after the study is completed.

When the study is completed, access to study data and/or samples will be provided through direct request to the University of North Carolina at Chapel Hill.

